4.3 Other Changes to Planned Analysis

- The protocol (Section 6.2.3) states that Total IgG against the full-length SARS-CoV-2 recombinant spike protein and/or spike protein subunits will be assessed using an immune-Luminex and/or ELISA assay. Instead, total IgG against the full-length SARS-CoV-2 recombinant spike protein, spike protein receptor binding domain (RBD) and spike protein

nucleocapsid (N) antigen have been assessed using an electrochemiluminescence (ECL) assay based on Meso-Scale Discovery (MSD) multiplex technology.

- The protocol defines seroconversion as ‘an antibody titer above 20 for participants that are seronegative at baseline and as a 4-fold increase in antibody titer from baseline for participants that are seropositive at baseline’. However, this definition is not suitable for the assays being used. Therefore, for this interim analysis seroconversion will be defined as a 4-fold increase from baseline in antibody titer/concentration. An additional analysis at a threshold of 2-fold increase from baseline will also be performed. Baseline is defined in Section 5.3.1.

4.4 Data to be Evaluated at This Interim Analysis

- Safety data will be available for all participants in Cohorts 1 and 2 (see Section 5.2 for description of cohorts).
 - For participants in Cohort 1a, safety data will be presented from Day 1 in Study ARCT-021-02 up to the data cut point for this interim analysis. Any safety data prior to Day 1 in this study will have been captured in the EDC as medical history.
 - For participants in Cohorts 1b and 2, safety data will be presented from the time of exiting the Parent Study (ARCT-021-01) up to the data cut point for this interim analysis. For participants in Cohort 1b, the safety data from the time of exiting the parent study up to Day 1 in Study ARCT-021-02 will be presented separately to the safety data following Day 1 (as participants receive an additional dose of study vaccine on Day 1).
- Immunogenicity data is not yet available for all assays/all cohorts. The data that will be evaluated at this interim is as follows (Table 2):
 - For Participants in Cohort 1a, immunogenicity data from Day 1, Day 29 and Day 57 in Study ARCT-021-02 (i.e., the only time points for which immunogenicity data is available for this cohort in ARCT-021-02) will be presented.
 - For participants in Cohorts 1b:
 - Immunogenicity data from the Parent Study for tests using the same assays as being performed in ARCT-021-02 is available only for participants in Cohorts 1b (B), 1b (D1), and 1b (D2). For these participants the Parent Study data will be presented together with the data from Day1, Day 29 and Day 57 in Study ARCT-021-02 (i.e., the time points for which immunogenicity data is available for these cohorts in ARCT-021-02). For all other participants in Cohort 1b, only immunogenicity data from Day1, Day 29 and Day 57 in Study ARCT-021-02 will be presented.
 - The proportion of participants seroconverting for neutralizing antibodies and binding antibodies against the SARS-CoV-2 Spike glycoprotein and against receptor binding domain of the SARS-CoV-2 spike glycoprotein will be assessed at Day 29 and Day 57. This is an additional analysis to those specified in the protocol.

- For participants in Cohort 2, immunogenicity data from the Parent Study for tests using the same assays as being performed in ARCT-021-02 is available only for participants in Cohorts 2 (D1), 2 (D2), 2 (E) and 2 (G). For these participants the Parent Study data will be presented together with the data from Day 29 in Study ARCT-021-2 (Day 29 is the only time point for which data is available for these cohorts in ARCT-021-02). For the remaining participants in Cohort 2 only data from Day 29 in Study ARCT-021-02 will be presented, as this is the only data (from the relevant assays) available at the time of this interim.

Table 2: Immunogenicity Data to be Included in Interim Analysis #1

Study/Time Point	Cohort/Sub-Cohort								
	1a	1b (A/C)	1b (B)	1b(D1/D2)	2 (A/C)	2 (B)	2 (D1/D2)	2 (E/G)	2 (F/H)
Parent Study									
Day 1	NA	NA	NA	X	NA	NA	X	X	X
Day 29	NA	NA	NA	X	NA	X	X	NA	X
Day 43	NA	NA	NA	X	NA	NA	X	X	X
Day 57	NA	NA	X	X	NA	NA	X	X	X
Day 85	NA	NA	NA	NA	NA	NA	NA	X	X
ARCT-021-02									
Day 1	X	X	X	X	NA	NA	NA	NA	NA
Day 29	X	X	X	X	X	X	X	X	X
Day 57	X	X	X	X	NA	NA	NA	NA	NA

NA = Not available/not applicable

5. GENERAL CONSIDERATIONS FOR DATA ANALYSIS

As there is no comparator group, there will be no formal hypothesis testing and therefore most of the statistical summaries will be descriptive and through displays of the data.

For this interim analysis, the following conventions will be used:

- Safety data:
 - All adverse event data reported for participants in Cohort 1a prior to Day 1 of study ARCT-021-02 are handled as medical history in the ARCT-021-02 study. The site was instructed to enter all medical history and ongoing adverse events from study ARCT-021-01 as medical history in this study.
 - All adverse event data reported for participants in Cohort 1b and Cohort 2 (all

subgroups) prior to Day 1 are handled as adverse events in the ARCT-021-02 study. For Cohort 1b, adverse event data occurring since end of study participation in ARCT-021-01 are summarized as adverse events but analyzed separately from those recorded in study ARCT-021-02 for the purpose of this analysis (since these participants received study vaccine in this study). For participants in Cohort 2, adverse event data occurring since end of study participation in ARCT-021-01 will be merged with AE data from Study ARCT-021-02 for the purposes of tabular presentation (since these participants do not receive additional study vaccine in this study)

- Immunogenicity data
 - Seroconversion will be defined as a 4-fold increase from baseline (Section 5.3.1) in antibody titer/concentration. An additional analysis at a threshold of 2-fold increase from baseline will also be performed.
 - Seropositivity at participant level for any timepoint (including baseline) is defined as a detectable level above LLOQ at that time point.

The summary statistics will consist of absolute and relative frequencies (percentages) for categorical variables and mean, median, standard deviation, minimum, maximum as well as number of non-missing observations will be used for discrete and continuous variables. For titers, geometric mean and 95% confidence intervals (CIs) will also be provided, as well as the percent geometric coefficient of variation (%GCV).

Summary statistics will also be provided for change from baseline using mean, median, standard deviation, minimum and maximum as well as the number of non-missing observations. Where applicable, the percentage change from baseline will be provided. For titer, geometric mean fold rise and 95% CIs will also be provided, as well as the %GCV.

Summary results will be provided for each population, and by cohort, and sub-cohort for Immunogenicity

Analyses will be performed using SAS for Windows statistical software, version 9.4 or higher (SAS, Cary, NC), except where other software may be deemed more appropriate.

CTI Clinical Trial and Consulting Services (Covington, KY) will perform all efficacy and safety statistical analyses.

Participant data will be listed and sorted by participant number and cohort/subcohort (see Section 5.2 for a description of cohort/sub-cohorts).

5.1 Data Quality Assurance

Efforts were made to perform source data verification, query resolution and data base lock prior to conducting the interim analysis. However, this is an unplanned interim analysis to support a regulatory filing that was not anticipated at the time of study initiation, and due to the short timeline, it was not possible to complete these activities. Therefore, data are to be pulled by CTI Biostatistics for interim analyses at a time when source verification and query resolution is still ongoing.

No changes will be made to this interim analysis SAP after the data is pulled for analysis.

All SAS programs used to create analysis data sets, tables, and listings are double programmed. The SAS outputs will be compared and the programs will be updated until the outputs match. Statistical outputs will be reviewed for consistency with the shells, accuracy, and consistency across outputs by a senior member of the Biostatistics team.

5.2 Analysis Sets

The following analysis sets are defined for this interim analysis:

Safety Population: All participants who receive Study vaccine in ARCT-021-02 only.

Longitudinal Safety Population: All participants who receive Study vaccine in either ARCT-021-01 or ARCT-021-02

Immunogenicity Population: All participants who receive Study vaccine in either ARCT-021-01 or ARCT-021-02 and who have evaluable immunogenicity data following first vaccine administration.

Within these populations, analyses will also include Cohorts that combine relevant safety and immunogenicity assessments across ARCT-021-01 and ARCT-021-02 according to time since administration of last dose of ARCT-021. These cohorts are defined as follows.

Two primary cohorts will be defined:

- Cohort 1: ARCT-021-02 vaccinated participants (those participants who receive ARCT-021 in Study ARCT-021-02, including those who were assigned to receive placebo in the parent study (ARCT-021-01) and those who enter the ARCT-021-02 without detectable neutralizing antibody responses at baseline)

This cohort will be further subdivided into additional sub-cohorts for all analyses:

- Cohort 1a: Primary vaccination (i.e., those participants whose first ARCT-021 vaccine administration occurs in the ARCT-021-02 study) and
- Cohort 1b: Booster vaccination (i.e., those participants who received primary vaccination in the ARCT-021-01 study and who receive an additional dose of ARCT-021 in the ARCT-021-02 study). Cohort 1b will be subdivided as follows for data analysis and presentation:
 - Cohort 1b (A): Participants that were in Cohort A (1 mcg single dose younger adult cohort) in the Parent Study
 - Cohort 1b (B): Participants that were in Cohort B (5 mcg single dose younger adult cohort) in the Parent Study
 - Cohort 1b (C): Participants that were in Cohort C (10 mcg single dose younger adult cohort) in the Parent Study
 - Cohort 1b (D1): Participants that were in Cohort D1 (7.5 mcg single dose younger adult cohort) in the Parent Study
 - Cohort 1b (D2): Participants that were in Cohort D2 (7.5 mcg single dose older adult cohort) in the Parent Study

- Cohort 2: ARCT-021-01 vaccinated participants (i.e., those participants who were vaccinated with ARCT-021 in the parent study and who do not receive subsequent vaccination with ARCT-021 in the current extension study). Cohort 2 will be subdivided as follows for data analysis and presentation:
 - Cohort 2 (A): Participants that were in Cohort A (1 mcg single dose younger adult cohort) in the Parent Study
 - Cohort 2 (B): Participants that were in Cohort B (5 mcg single dose younger adult cohort) in the Parent Study
 - Cohort 2 (C): Participants that were in Cohort C (10 mcg single dose younger adult cohort) in the Parent Study
 - Cohort 2 (D1): Participants that were in Cohort D1 (7.5 mcg single dose younger adult cohort) in the Parent Study
 - Cohort 2 (D2): Participants that were in Cohort D2 (7.5 mcg single dose older adult cohort) in the Parent Study
 - Cohort 2 (E): Participants that were in Cohort E (5 mcg two dose younger adult cohort) in the Parent Study
 - Cohort 2 (F): Participants that were in Cohort F (3 mcg two dose younger adult cohort) in the Parent Study
 - Cohort 2 (G): Participants that were in Cohort G (5 mcg two dose older adult cohort) in the Parent Study
 - Cohort 2 (H): Participants that were in Cohort H (3 mcg two dose older adult cohort) in the Parent Study

NOTE: in the above descriptions ‘younger adult’ refers to participants 21 – 55 years and ‘older adult’ refers to participants 56 – 80 years, with the ages being counted at the time of enrolment into the Parent Study.

5.3 Assessment Windows and Visits Variables Derivations.

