Subjects that are not receiving ARCT-021 in this study

All participants who received 2 injections of ARCT-021 as part of participation in Cohorts E, F, G, and H in Study ARCT-021-01 and any participant who received 1 injection of ARCT-021 in Cohorts A, B, C, D1 and D2 in Study ARCT-021-01 AND who is seropositive by SARS-CoV-2 PRNT50 neutralising antibody test at screening in this study (ARCT-021-02).

The study comprises an up to a 4-week Screening Period followed by a 9-month observation period. The length of each subject's participation is approximately 10 months from screening to last study visit.

After screening subjects will return for outpatient visits on Days 1, 29, 85, 197 and then 281. The final visit will be on Day 281.

Subjects that do not receive ARCT-021 in this study will not have any further laboratory safety evaluations performed in this study and only Serious Adverse Events (SAE) and Medically Attended AE (MAAE) will be recorded. Subjects will be instructed to contact the study site staff immediately if they experience an adverse event that requires them to seek medical attention or if they become hospitalised.

Subjects receiving ARCT-021

All participants who received placebo as part of participation in Study ARCT-021-01 and any participant who received 1 injection of ARCT-021 in Cohorts A, B, C, D1 and D2 in Study ARCT-021-01 AND who is seronegative by SARS-CoV-2 PRNT50 neutralising antibody test at screening in this study (ARCT-021-02).

Blood and urine samples will be collected for safety evaluations up to 28 days after the last injection of ARCT-021 ([Appendix 1](#)).

Local and systemic solicited and unsolicited AEs will be recorded daily by the subject in a symptom diary for at least 7 days post vaccination and up to 14 days post vaccination if any events are persisting at 7 days (Section [6.2.1](#) and [Appendix 1](#)).

[figure not shown]

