	
Seroconversion will be assessed across a range of dilutions and will be defined as an antibody titer above 20 for subjects that are seronegative at baseline and as a 4-fold increase in antibody titer from baseline for subjects that are seropositive at baseline.
 
T-cell subclass responses will be tested by flow cytometry and ELISPOT assay using peptide pools from SARS CoV-2 spike protein.

Sponsor	Arcturus Therapeutics, Inc.

STUDY DESIGN AND TREATMENT SCHEMA FOR SUBJECTS NOT RECEIVING ARCT-021

STUDY DESIGN AND TREATMENT SCHEMA FOR SUBJECTS RECEIVING A SINGLE INJECTION OF ARCT-021

STUDY GLOSSARY

Abbreviation	Definition
3'	On the 3-prime end of the nucleotide sequence
5'	On the 5-prime end of the nucleotide sequence
AE	Adverse event
AESI	Adverse Event of Special Interest
ALP	Alkaline phosphatase
ALT	Alanine aminotransferase (SGPT)
aPTT	Activated partial thromboplastin time
ARCT-021	Investigational drug product comprising mRNA-2002 (coding for SARS-CoV-2 full length spike glycoprotein) formulated in the LUNAR® lipid nanoparticle delivery system
ARCT-810	Investigational drug product comprising mRNA-1801 (coding for human ornithine transcarbamylase enzyme) formulated in the LUNAR® lipid nanoparticle delivery system
ARDS	Acute respiratory distress syndrome
AST	Aspartate aminotransferase (SGOT)
AUC	Area under the curve
Bb	Complement factor Bb (activated complement split product)
βhCG	Beta-subunit of human chorionic gonadotropin (pregnancy test)
BP	Blood pressure
BUN	Blood urea nitrogen
C	Centigrade
C3	Complement factor 3
C3a	Complement factor C3a (activated complement split product)
C4	Complement factor 4
C4a	Complement factor C4a (activated complement split product)
C5a	Complement factor C5a (activated complement split product)
CBC	Complete blood count
CESI	Clinical Event of Special Interest
CMV	Cytomegalovirus
CNS	Central nervous system

COVID-19	Coronavirus disease 2019, the disease caused by SARS-CoV-2 virus infection.
CRF	Case report form
CRP	C-reactive protein
CS	Clinically significant
CV	Cardiovascular
DL	Deciliter
DNA	Deoxyribonucleic acid
DSPC	1,2-distearoyl-sn-glycero-3-phosphocholine
ECG	Electrocardiogram
eCRF	Electronic Case Report Form
EDC	Electronic data capture
ED ₅₀	50% effective dose
ELISA	Enzyme-linked immunosorbent assay
ESR	Erythrocyte sedimentation rate

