2.2.2 Secondary Endpoints

Immunogenicity

1. Mean and geometric mean titer or concentration (GMT, GMC) and the geometric mean fold rise (GMFR) in SARS-CoV-2 neutralizing antibodies and in binding antibody against the SARS-CoV-2 Spike glycoprotein and against receptor binding domain of the SARS-CoV-2 spike glycoprotein, at multiple time points in each cohort.
2. Proportion of ARCT-021-naïve participants (Cohort 1a; see Section 5.2 for description of cohorts)

seroconverting for neutralizing antibodies and binding antibodies against the SARS-CoV-2 Spike glycoprotein and against receptor binding domain of the SARS-CoV-2 spike glycoprotein will be assessed at multiple time points.

The proportion of ARCT-021 boosted participants (Cohort 1b) seroconverting for neutralizing antibodies and binding antibodies against the SARS-CoV-2 Spike glycoprotein and against receptor binding domain of the SARS-CoV-2 spike glycoprotein will also be assessed at multiple time points. This is an additional analysis to those specified in the protocol.

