2. Proportion of ARCT-021-naïve participants seroconverting for neutralizing antibodies and IgG antibodies against the full-length SARS-CoV-2 recombinant spike protein antigen and spike protein RBD will be assessed at the above mentioned time points. Seroconversion will be defined as a 4-fold increase in antibody titer/concentration from baseline. An additional analysis at a threshold of 2-fold increase from baseline will also be performed.

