7.3 Immunogenicity Endpoint Summaries

Participants with evidence of SARS-CoV-2 infection or that received an off-study vaccine will be censored from the immunogenicity analysis for all timepoints and evaluations beyond earlier of the time point at which evidence of SARS-CoV-2 infection occurred or the time point at which off-study vaccine was received. Evidence of SARS-CoV-2 infection includes a positive PCR test or a positive antinucleocapsid antibody test (defined as a concentration $\geq 5,000$ AU/ml)

The timepoints for analysis of each of the immunogenicity parameters is shown in Appendix 9.1.

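### SAP 5 defines baseline seropositivity but SAP 7.2–7.3 never use it, so any Cohort 1a participant with Day 1 antibody whom the SAP 7.3 infection rule does not catch stays in the pooled results

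*SAP*

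**What the plan says.** **Cohort and endpoint.** SAP 5.2 defines "Cohort 1a: Primary vaccination (i.e., those participants whose first ARCT-021 vaccine administration occurs in the ARCT-021-02 study". There is no condition on serostatus or infection history. SAP 2.2.2 makes this cohort the population for a secondary endpoint: "Proportion of ARCT-021-naïve participants (Cohort 1a; see Section 5.2 for description of cohorts".

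**Serostatus.** SAP 5 states: "Seropositivity at participant level for any timepoint (including baseline) is defined as a detectable level above LLOQ at that time point". The SAP revision table shows that this definition was added because it had been missing. SAP 7.2, 7.3 and their subsections do not refer to it again.

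**Seroconversion.** In the protocol synopsis (Immunogenicity), the rule depended on baseline: it was "defined as an antibody titer above 20 for subjects that are seronegative at baseline", and a 4-fold rise for those seropositive at baseline. SAP 4.3 calls this unsuitable for the assays in use and replaces it. SAP 7.2 now reads: "Seroconversion will be defined as a 4-fold increase in antibody titer/concentration from baseline". A 2-fold threshold is an additional analysis.

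**Infection.** SAP 7.3 states: "Participants with evidence of SARS-CoV-2 infection or that received an off-study vaccine will be censored from the immunogenicity analysis for all timepoints and evaluations" beyond the earlier of the two events. "Evidence of SARS-CoV-2 infection includes a positive PCR test or a positive antinucleocapsid antibody test", with positivity set at 5,000 AU/ml or more.

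**Who is dosed.** The protocol synopsis, under the heading for subjects receiving ARCT-021, lists "All participants who received placebo as part of participation in Study ARCT-021-01 and any participant who received 1 injection of ARCT-021", and the seronegative condition follows the single-injection group. The dosage section of the synopsis, protocol 3.2 and SAP 3.2 name placebo and single-injection recipients together before stating the condition, so it can be read as covering both.

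**The concern.** Cohort 1a is meant to show the response to a first dose of ARCT-021. A placebo recipient who already carries antibody to SARS-CoV-2 when dosed is making a recall response. Pooled with the rest, that person tends to raise the post-dose GMT. The effect on GMFR and seroconversion depends on how far a high starting value can still rise.

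The protocol's seroconversion rule took baseline status into account. After SAP 4.3, baseline status enters no described result, although the SAP went on to define it. The cohort is small and the interim supports a regulatory filing (SAP 4), so one or two such participants could be visible in the summary without a reader knowing it.

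**Working it through.** The documents give no size for Cohort 1a, no count of baseline-seropositive participants and no expected titre, so there is no planned figure to reproduce. Steps 1 and 2 compare passages. Steps 3 to 5 use assumed inputs, marked as such.

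**1. Can a seropositive placebo recipient enter Cohort 1a?**
- The synopsis list of dosed subjects reads most naturally as including all placebo recipients. The dosage text, protocol 3.2 and SAP 3.2 can be read either way.
- The undosed groups (synopsis, protocol 3.2, SAP 3.2) are two-injection recipients and seropositive single-injection recipients. No undosed path is described for a seropositive placebo recipient.
- Protocol 5.2 does not list prior SARS-CoV-2 infection as an exclusion; criterion 14 is a discretionary catch-all.
- Entry is therefore possible but not established. Even if the condition covers placebo recipients, screening uses PRNT50, whereas SAP 7.2 analyses pseudovirus neutralisation and MSD binding assays. A PRNT50-negative person may still be above LLOQ on those.

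**2. Whom does SAP 7.3 remove?**
- Anti-N is on the MSD panel (SAP 7.2, 7.3.1.1), and Day 1, Day 29 and Day 57 are the Cohort 1a time points (SAP 4.4, Table 2).
- A participant with anti-N of 5,000 AU/ml or more at Day 1 is, on the natural reading, out at Day 29 and Day 57.
- A participant above LLOQ for neutralising, spike or RBD antibody at Day 1, with anti-N below 5,000 AU/ml and no positive PCR, stays.
- The rule acts beyond the time point of evidence. It does not say how earlier evidence is treated, and it leaves the Day 1 value in the baseline summary. For placebo recipients, infections between the two studies are recorded as medical history (SAP 6.3), so the source of that evidence also needs naming.

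**3. Effect on GMT.** If k of n participants remain with titres R times those of the others, pooled GMT / GMT of the others = R^(k/n). Assumed: n = 28 or 20, R = 10 to 40; k counts people left after SAP 7.3.

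| n | k | R = 10 | R = 40 |
|---|---|---|---|
| 28 | 0 | 1.00 | 1.00 |
| 28 | 1 | 10^(1/28) = 1.09 | 40^(1/28) = 1.14 |
| 28 | 2 | 10^(2/28) = 1.18 | 40^(2/28) = 1.30 |
| 20 | 2 | 10^(2/20) = 1.26 | 40^(2/20) = 1.45 |

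**4. How much SAP 7.3 helps.** If a share f of the cohort was previously infected and the rule catches a share s of them, the share left is f(1 − s)/(1 − fs). With assumed f = 10% and R = 10:
- no censoring: 10^0.10 = 1.26
- s = 50%: share left 0.0526, factor 1.13
- s = 70%: share left 0.0323, factor 1.08
- s = 90%: share left 0.0110, factor 1.03
- s = 100%: factor 1.00

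**5. Effect on seroconversion.** SAP 5.4 recodes titres below LLOQ to LLOQ/2.
- From that baseline the 4-fold threshold is 4 × LLOQ/2 = 2 × LLOQ, and the 2-fold threshold is 2 × LLOQ/2 = LLOQ.
- From a baseline of 10 × LLOQ they are 40 × LLOQ and 20 × LLOQ.

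The pooled rate is p(naive) × (1 − f) + p(pre-immune) × f. With assumed p(naive) = 0.90 and f = 10%:
- p(pre-immune) = 0.20 gives 0.81 + 0.02 = 0.83
- p(pre-immune) = 1.00 gives 0.81 + 0.10 = 0.91

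The direction is not fixed.

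**The case against.** A reader might infer that previously infected placebo recipients pass unchecked into the Cohort 1a results. The documents do not support that. SAP 7.3 is a real filter, and step 4 shows that a sensitive one removes most of the effect. What stands is that the filter is blind to anti-N below 5,000 AU/ml and is not explicit about evidence on or before Day 1.

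Other defences also have force:
- The endpoint says ARCT-021-naïve, meaning vaccine-naïve, so the cohort label is correct.
- The 4-fold requirement for baseline-seropositive subjects comes from the protocol. The SAP changed only the rule for seronegative subjects, disclosed the change, gave a reason and added a 2-fold analysis.
- A reader might infer that GMT and seroconversion are distorted in opposite directions. Step 5 shows that this depends on the response rate assumed for pre-immune people.
- A reader might infer a biased comparison of Cohorts 1a and 1b. SAP 5 has no comparator and no hypothesis testing, so no such contrast is planned.
- In Cohort 1b, Day 1 antibody from the earlier ARCT-021 dose is to be expected in a booster group and is not contamination.
- Results are listed by participant and time point, GMFR uses each person's own baseline, and the table shells are not among the documents. Whether a shell already splits by serostatus cannot be checked.

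None of this puts the baseline definition to use in the SAP text, and listings do not give a summary for seronegative participants.

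**Conclusion.** The point holds as a low-cost improvement, not as an error that undermines the interim. Cohort 1a is set by vaccine history, the SAP's own baseline serostatus definition feeds no analysis that the SAP describes, and a narrow group of pre-immune participants can stay in the pooled results.

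The size is unknown. If nobody is in that group, nothing changes. If one or two of 28 remain after censoring, with titres 10- to 40-fold higher, the GMT rises by about 9% to 30%. The cohort size, the counts and the fold differences are all assumptions, chosen only to show scale. No direction can be given for seroconversion. Separately, the wording on dosing of placebo recipients is open to two readings and must be reconciled; I take no position on which is right.

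**What to change.** In SAP 7.2 and 7.3:
- Report, by assay, the number seropositive at Day 1 in Cohorts 1a and 1b, using the SAP 5 definition. For Cohort 1b this count is enough.
- For Cohort 1a, give GMT/GMC, GMFR and seroconversion (4-fold and 2-fold) for baseline-seronegative participants beside the all-participant result.
- Flag baseline-seropositive participants in the listings.
- State that the SAP 7.3 censoring covers evidence of infection dated on or before Day 1, and that for placebo recipients this includes infections recorded as medical history.

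Reconcile the protocol synopsis and section 3.2 with SAP 3.2 on whether the seronegative condition applies to placebo recipients.

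The cost is one more table and some small cells; the Day 1 values are already in the planned data (SAP Table 2). SAP 5.1 bars changes after the data pull, so this must be made before it or go into the SAP for the final analysis.
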